10.4 Tissue Banking

Leftover pancreatic fluid, tissue, and fecal samples will be stored and maintained for future research. Banked samples for use in future research will include blood (20 mL collected from the participant at each visit), and surplus pancreatic fluid, tissue, and fecal samples leftover after all study analyses are completed. Future research may include: 1) studies to identify genes and/or biomarkers and proteins that influence an individual's risk of getting pancreatitis, pancreatic cancer, or other diseases; 2) studies to identify specific pathways and mechanisms that promote pancreatic cancer. All banked specimens will be coded with the unique Biobank subject identifier and stored in -80°C freezers located in the Shuman Basement of the Davis Research Building at CSMC.

Appropriate administrative, physical, and technical safeguards are in place to ensure the confidentiality, integrity, and security of the banked specimens. Investigators with future IRB approved studies who are approved to receive specimens will not be given access to any information that can establish the identity of the donor. All data and specimens sent to approved investigators will be coded and de-identified, and will contain no direct identifiers. The data will always be published using aggregate statistics and no participant will be identified in any reports or publications.

Biologic specimens collected during the conduct of each clinical trial that are not used during the course of the study will be considered deliverables under the contract and thus the property of the NCI. At study completion, NCI reserves the option to either retain or relinquish ownership of the unused biologic specimens. If NCI retains ownership of specimens, the Contractor shall collect, verify and transfer the requested biologic specimens from the site to a NCI-specified repository or laboratory at NCI's expense.

11. REPORTING ADVERSE EVENTS

DEFINITION: AE means any untoward medical occurrence associated with the use of a drug in humans, whether or not considered drug related. An AE can therefore be any unfavorable and unintended sign), symptom, or disease temporally associated with participation in a study, whether or not related to that participation. This includes all deaths that occur while a participant is on a study.

Please note that all abnormal clinical laboratory values that are determined to be of clinical significance based on a physician's assessment are to be reported as AEs. Those labs determined to be of no clinical significance or of unknown clinical significance (per the physician's assessment) should not be reported as AEs. Any lab value of unknown clinical significance should continue to be investigated/followed-up further for a final determination, if possible.

A list of AEs that have occurred or might occur can be found in §6.2 Reported Adverse Events and Potential Risks, as well as the Investigator Brochure or package insert.

11.1 Adverse Events

11.1.1 Reportable AEs

All AEs that occur after the informed consent is signed and Study Visit 1 (baseline) assessments are completed must be recorded on the AE CRF (paper and/or electronic) whether or not related to study agent.

11.1.2 AE Data Elements:

The following data elements are required for adverse event reporting.

- AE verbatim term
- NCI Common Terminology Criteria for Adverse Events version 4.0 (CTCAE v4.0) AE term (MedDRA lowest level term)
- CTCAE (MedDRA) System Organ Class (SOC)
- Event onset date and event ended date
- Treatment assignment code (TAC) at time of AE onset
- Severity grade
- Attribution to study agent (relatedness)
- Whether or not the event was reported as a serious adverse event (SAE)

- Whether or not the subject dropped due to the event
- Outcome of the event

11.1.3 Severity of AEs

11.1.3.1 Identify the AE using the CTCAE version 4.0. The CTCAE provides descriptive terminology (MedDRA lowest level term) and a grading scale for each AE listed. A copy of the CTCAE can be found at http://ctep.cancer.gov/protocolDevelopment/electronic_applications/ctc.htm.

AEs will be assessed according to the grade associated with the CTCAE AE term. AEs that do not have a corresponding CTCAE term will be assessed according to the general guidelines for grading used in the CTCAE v4.0. as stated below.

CTCAE v4.0 general severity guidelines:

Grade	Severity	Description
1	Mild	Mild; asymptomatic or mild symptoms; clinical or diagnostic observations only; intervention not indicated.
2	Moderate	Moderate; minimal, local or noninvasive intervention indicated; limiting age-appropriate instrumental activities of daily living (ADL)*.
3	Severe	Severe or medically significant but not immediately life-threatening; hospitalization or prolongation of hospitalization indicated; disabling; limiting self-care ADL**.
4	Life-threatening	Life-threatening consequences; urgent intervention indicated.
5	Fatal	Death related to AE.

ADL

*Instrumental ADL refers to preparing meals, shopping for groceries or clothes, using the telephone, managing money, *etc.*

**Self-care ADL refers to bathing, dressing and undressing, feeding self, using the toilet, taking medications, and not bedridden.

11.1.4 Assessment of relationship of AE to treatment

The possibility that the adverse event is related to study agent will be classified as one of the following: not related, unlikely, possible, probable, definite.

11.1.5 Follow-up of AEs

All AEs, including lab abnormalities that in the opinion of the investigator are clinically significant, will be followed according to good medical practices and documented as such. Adverse Events which occur in participants who are screened but not enrolled in the study will be followed for one week.

11.2 Serious Adverse Events

11.2.1 DEFINITION: Regulations at 21 CFR §312.32 (revised April 1, 2014) defines an SAE as any untoward medical occurrence that at any dose has one or more of the following outcomes:

- Death
- A life-threatening AE
- Inpatient hospitalization or prolongation of existing hospitalization
- A persistent or significant incapacity or substantial disruption of the ability to perform normal life functions
- A congenital abnormality or birth defect
- Important medical events that may not be immediately life-threatening or result in death or hospitalization should also be considered serious when, based upon appropriate medical judgment, they may jeopardize the patient and may require intervention to prevent one of the other outcomes.

11.2.2 Reporting SAEs to DCP

11.2.2.1 The Lead Organization and all Participating Organizations will report SAEs on the DCP SAE Report Form found at <http://prevention.cancer.gov/clinical-trials/clinical-trials-management/protocol-information-office/pio-instructions-and-tools/2012-consortia>.

11.2.2.2 Contact the DCP Medical Monitor by phone within 24 hours of knowledge of the event.

DCP Medical/Task Order Monitor
[name] [name], FACS
NCI/Division of Cancer Prevention
[name]
[name]
[name]
[contact]
[contact]
Email: [contact]

Include the following information when calling the Medical Monitor:

- Date and time of the SAE
- Date and time of the SAE report
- Name of reporter
- Call back phone number
- Affiliation/Institution conducting the study
- DCP protocol number
- Title of protocol
- Description of the SAE, including attribution to drug and expectedness

11.2.2.3 The Lead Organization and all Participating Organizations will email written SAE reports to the following within 48 hours of learning of the event using the fillable PDF SAE Report Form.

- DCP's Regulatory Contractor CCS Associates, Inc. (CCSA; [contact]) at [contact]
- NCI DCP Medical Monitor, [name] ([contact])
- Northwestern Cancer Prevention Consortium ([contact])

11.2.2.4 The DCP Medical Monitor and CCSA regulatory staff will determine which SAEs require FDA submission as IND safety reports.

11.2.2.5 The Lead Organization and all Participating Organizations will comply with applicable regulatory requirements related to reporting SAEs to the IRB/IEC.

11.2.3 Follow-up of SAE

Site staff should send follow-up reports as requested when additional information is available. Additional information should be entered on the DCP SAE Report Form in the appropriate format. Follow-up information should be sent to DCP as soon as available. All SAEs will be followed according to standard of care. SAEs possibly, probably, or definitely related to the study agent will be followed until resolved.

12. STUDY MONITORING

12.1 Data Management

Data will be managed by the study statistician, [name], according to standard operating procedures, which meet the guidelines of DCP Requirements for Data Management and which follow the Data Management Plan that Northwestern University has on file with the Division of Cancer Prevention, NCI. Source data verification will be performed by the Northwestern Cancer Prevention Consortium. The Consortia 2012 Data Management Plan, submitted as part of a contract agreement with the NCI (HHSN261201200035I), was approved.

Clinical data will be reported to Northwestern University through the Lurie Cancer Center Clinical Trials Management System (CTMS), which will be the database of record.

12.2 Case Report Forms

Participant data will be collected using protocol-specific case report forms (CRFs) developed from the standard set of DCP Chemoprevention CRF Templates and utilizing NCI-approved Common Data Elements (CDEs). The approved CRFs will be used by Northwestern University to create the electronic CRFs (e-CRFs) screens in the CTMS-RDC application. Site staff will enter data into the e-CRFs for transmission to DCP according to DCP standards and procedures.

All specimen results that are batch analyzed will be collected and stored on excel spreadsheets. The excel spreadsheets will constitute the database of record.

12.3 Source Documents

All source documents will be collected and stored by the research staff at the site of accrual. Any data recorded directly in CTMS that constitute no prior written or electronic record of data, will be specifically identified as source data. Quality of Life questionnaires completed in person may be completed on the paper and entered into CTMS.

12.4 Data and Safety Monitoring Plan

A comprehensive Data Safety and Monitoring Plan has been submitted by Northwestern University, approved by the DCP, and is on file there. Any future changes will be forwarded for review.

This trial is subject to review by the Lurie Cancer Center Data Monitoring Committee (DMC). Semi-Annual reports, SAEs, and protocol deviations will be reviewed by the DMC at bi-weekly meetings. This trial is also subject to possible annual audits by the Lurie Cancer Center Clinical Trials Audit Committee (CTAC).

12.5 Sponsor or FDA Monitoring

The NCI, DCP (or their designee), pharmaceutical collaborator (or their designee), or FDA may monitor/audit various aspects of the study. These monitors will be given access to facilities, databases, supplies and records to review and verify data pertinent to the study.

12.6 Record Retention

Clinical records for all participants, including CRFs, all source documentation (containing evidence to study eligibility, history and physical findings, laboratory data, results of consultations, *etc.*), as well as IRB records and other regulatory documentation will be retained by the Investigator in a secure storage facility in compliance with Health Insurance Portability and Accountability Act (HIPAA), Office of Human Research Protections (OHRP), Food and Drug Administration (FDA) regulations and guidances, and NCI/DCP requirements, unless the standard at the site is more stringent. The records for all studies performed under an IND will be maintained, at a minimum, for two years after the approval of a New Drug Application (NDA). For NCI/DCP, records will be retained for at least three years after the completion of the research. NCI will be notified prior to the planned destruction of any materials. The records should be accessible for inspection and copying by authorized persons of the Food and Drug Administration. If the study is done outside of the United States, applicable regulatory requirements for the specific country participating in the study also apply.

12.7 Cooperative Research and Development Agreement (CRADA)/Clinical Trials Agreement (CTA)

The agent(s) supplied by DCP, NCI, used in this protocol, is/are provided to the NCI under a Collaborative Agreement (CRADA, CTA) between the Pharmaceutical Company(ies) (hereinafter referred to as Collaborator(s)) and the NCI Division of Cancer Prevention. Therefore, the following obligations/guidelines, in addition to the provisions in the “Intellectual Property Option to Collaborator@” contained within the terms of award, apply to the use of Agent(s) in this study:

12.7.1 Agent(s) may not be used for any purpose outside the scope of this protocol, nor can Agent(s) be transferred or licensed to any party not participating in the clinical study. Collaborator(s) data for Agent(s) are confidential and proprietary to Collaborator(s) and shall be maintained as such by the investigators. The protocol documents for studies utilizing investigational agents contain confidential information and should not be shared or distributed without the permission of the NCI. If a patient participating on the study or participant’s family member requests a copy of this protocol, the individual should sign a confidentiality agreement. A suitable model agreement can be downloaded from the DCP website.

12.7.2 For a clinical protocol where there is an Investigational Agent used in combination with (an) other investigational Agent(s), each the subject of different collaborative agreements, the access to and use of data by each Collaborator shall be as follows (data pertaining to such combination use shall hereinafter be referred to as "Multi-party Data").

12.7.3 NCI must provide all Collaborators with prior written notice regarding the existence and nature of any agreements governing their collaboration with NIH, the design of the proposed combination protocol, and the existence of any obligations that would tend to restrict NCI's participation in the proposed combination protocol.

12.7.4 Each Collaborator shall agree to permit use of the Multi-Party Data from the clinical trial by any other Collaborator solely to the extent necessary to allow said other Collaborator to develop, obtain regulatory approval, or commercialize its own investigational agent.

12.7.5 Any Collaborator having the right to use the Multi-Party Data from these trials must agree in writing prior to the commencement of the trials that it will use the Multi-Party Data solely for development, regulatory approval, and commercialization of its own investigational agent.

12.7.6 Clinical Trial Data and Results and Raw Data developed under a collaborative agreement will be made available exclusively to Collaborator(s), the NCI, and the FDA, as appropriate. All data made available will comply with HIPAA regulations.

12.7.7 When a Collaborator wishes to initiate a data request, the request should first be sent to the NCI, who will then notify the appropriate investigators of Collaborator's wish to contact them.

12.7.8 Any manuscripts reporting the results of this clinical trial must be provided to DCP for immediate delivery to Collaborator(s) for advisory review and comment prior to submission for publication. Collaborator(s) will have 30 days (or as specified in the CTA) from the date of receipt for review. Collaborator shall have the right to request that publication be delayed for up to an additional 30 days in order to ensure that Collaborator's confidential and proprietary data, in addition to Collaborator(s)'s intellectual property rights, are protected. Copies of abstracts must be provided to DCP for forwarding to Collaborator(s) for courtesy review as soon as possible and preferably at least three days prior to submission, but in any case, prior to presentation at the meeting or publication in the proceedings. Press releases and other media presentations must also be forwarded to DCP prior to release. Copies of any manuscript, abstract, and/or press release/ media presentation should be sent to the Protocol Information Office at [contact].

The Protocol Information Office will forward manuscripts to the DCP Project Officer for distribution to the Collaborator(s). No publication, manuscript or other form of public disclosure shall contain any of Collaborator's confidential/proprietary information.

13. STATISTICAL CONSIDERATIONS

13.1 Study Design/Description

This is a phase II randomized, double-blinded, placebo-controlled trial of statin to evaluate the impact of statin treatment on pancreatic function and inflammation implicated in pancreatic carcinogenesis in patients with recurrent acute pancreatitis. The primary objective of this study will be to demonstrate that statins will improve pancreatic function in high-risk patients, as defined by those with two or more episodes of acute pancreatitis in the past 12 months.

The primary outcome for this study is change from baseline (Study Visit 1) at 6 months of *peak bicarbonate concentration* as measured by *ePFT*. Sample size calculations follow from computations PASS 11 (www.ncss.com). Means and standard deviations of peak bicarbonate concentrations are derived from the literature on the validity and utility of *ePFT* for diagnosis of chronic pancreatitis [56, 57]. We expect baseline peak bicarbonate levels to be 60 mEq/L in these patients with recurrent pancreatitis, with a standard deviation of 13 mEq/L. We expect the peak bicarbonate levels to increase in both simvastatin and placebo groups as the groups recover from the acute pancreatitis event, with the simvastatin group showing a greater increase to full recovery compared to the placebo group. An analytic sample size of 24 (after 20% drop out) will have 82% power to detect a statistically significant one-sided difference of 15 mEq/L (25 vs. 10 mEq/L) at an alpha level of 0.05. The anticipated changes are well within the range of

peak bicarbonate levels of patients with mild to severe pancreatitis [56, 57] whose median peak bicarbonate levels range from 40 mEq/L to 100 mEq/L.

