13.3 Accrual and Feasibility

Sample size: Intervention = 30 (20:10) randomized sample; after 20% drop out = 24 (16:8) analytic sample. The expected accrual rate is 1-2 participants per month across four study sites, and the planned recruitment duration is 24 months. We anticipate that all evaluable participants will have completed all study procedures within three years. Power and precision arguments are provided below.

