13.4 Primary Objective, Endpoint(s), Analysis Plan

The primary outcome for this study is change from baseline (Study Visit 1) at 6 months of peak bicarbonate concentration as measured by ePFT. For the primary endpoint, we will consider differences D(T) and D(P) for D=After-Before, for Treatment and Placebo (Control) groups respectively. Then we will use a nonparametric two-sample Wilcoxon-Mann-Whitney test to address the hypothesis H0: mean [D (T)] =mean [D (P)] versus H1: mean[D(T)] > mean[D(P)], and report a one-sided p-value, as presented in Table 3. If p<0.05 we will consider this to be evidence of activity in the simvastatin group.

Table 3. Numeric Results for Mann-Whitney Test (Uniform Distribution)									
Power	N1	N2	Ratio	Alpha	Beta	Mean1	Mean2	S1	S2
0.82	16	8	0.5	0.05	0.18	25	10	13	13
Null Hypothesis: Mean1=Mean2. Alternative Hypothesis: Mean1>Mean2. The standard deviations were assumed to be equal at 13 mEq/L.									

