13.5 Secondary Objectives, Endpoints, Analysis Plans

For secondary endpoints, we will consider D(T) and D(P) as well as percent change relative to baseline as well, namely, D (T)/B (T) and D (P)/B (P). For all secondary variables, we will use descriptive statistics and graphics at 3 months and at 6 months, as well as study random effects regression trends along the timeline Baseline → 3 months → 6 months for further hypotheses generation. In particular, we will look into cytokines, chemokines, and adhesion molecules and quality of life scores from the QLQ-C30 and QLQ-PAN28(CP) assessment after possible log-transformation of continuous data. In particular, we will be interested in the relation between a) pairs of secondary variables and differences D=After-Before in pairs of secondary variables in the Treatment group, b) same as a) but in the control group, c) comparing pairwise changes between the Treatment and the Control groups, and d) relationship of secondary outcomes with recurrent pancreatitis. In this way, we will be able to study co-dependence among various secondary variables and their possible relationship with recurrent pancreatitis. We will thus fit various regression models, estimate relevant parameters (e.g., intercept, slope) and explore the apparent magnitudes of change in these parameters in the treatment and the control group.

Analyses will be performed with Stata software. All analyses will be conducted on an intention to treat basis (all randomized participants will be included in the assigned group) and will begin with univariate cross-sectional statistics for profiling the study population and bivariate tabulations as a preliminary step to possible model building. We will not control for overall Type I error due to small number of

observations and the preliminary nature of the study.

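### The stated 82% power is too high for the planned Mann-Whitney test at 16 vs 8 (about 75% exact, 77% by normal approximation on Table 3's own inputs), and the basis for the SD of change is not stated

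*Combined protocol and SAP*

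**What the plan says.** Section 13.1 gives the power claim: "An analytic sample size of 24 (after 20% drop out) will have 82% power to detect a statistically significant one-sided difference of 15 mEq/L", with mean changes of 25 and 10 mEq/L and "at an alpha level of 0.05". It names PASS 11 as the source of the calculation.

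Section 13.4 sets the primary analysis on the change from before to after treatment: "Then we will use a nonparametric two-sample Wilcoxon-Mann-Whitney test to address the hypothesis", reported one-sided, with p<0.05 taken as evidence of activity. Table 3, headed "Numeric Results for Mann-Whitney Test (Uniform Distribution)", lists power 0.82, Beta 0.18, N 16 and 8, means 25 and 10, and SDs 13 and 13.

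On the SD, section 13.1 says: "We expect baseline peak bicarbonate levels to be 60 mEq/L in these patients with recurrent pancreatitis, with a standard deviation of 13 mEq/L". The note under Table 3 says: "The standard deviations were assumed to be equal at 13 mEq/L". Section 13.1 attributes the means and SDs of bicarbonate concentrations to two literature references.

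Section 13.3 tells the reader: "Power and precision arguments are provided below". Section 13.5 adds: "Analyses will be performed with Stata software". No section says whether the primary p-value will be exact or approximate.

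**The concern.** The 82% is what the two-sample t-test gives for these inputs. For uniform data the large-sample efficiency of Mann-Whitney relative to the t-test is 1, so a formula that relies on it returns the t-test power unchanged. With eight placebo patients that equality need not hold.

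The SD raises a second question. A value introduced as the spread of baseline levels between patients is used for within-patient change. These are different quantities, and the ratio of one to the other depends on a correlation that the plan does not give.

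Section 13.3 promises power and precision arguments, but no precision calculation follows. Table 3 is therefore the only support for the sample size, and a non-significant result would naturally be read against its 18% type II error. The unnamed p-value version also leaves open a choice that could decide a borderline primary result.

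**Working it through.** **Inputs (sections 13.1, 13.3 and 13.4).** n1 = 16, n2 = 8; difference in mean change 25 − 10 = 15 mEq/L; SD 13 in both arms; one-sided alpha 0.05; uniform distribution; Mann-Whitney test on change scores.

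**Step 1: reproduce the plan's figure.** For the one-sided two-sample t-test:

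- standardized difference = 15/13 = 1.154
- noncentrality = 1.154 × √(16 × 8/24) = 2.665, with 22 degrees of freedom
- power = 0.8255

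This agrees with the stated 0.82. The documents do not show the formula that PASS used, so attributing 0.82 to this route is an inference from the match.

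**Step 2: rejection rules of the planned test.** Under the null, U has mean 16 × 8/2 = 64 and variance 16 × 8 × 25/12 = 266.7 (SD 16.33). From the exact null distribution:

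| Version | Rejects at | True one-sided size |
|---|---|---|
| Exact | U ≥ 92 | 0.0463 |
| Normal approximation, no continuity correction | U ≥ 91 | 0.0528 |
| Normal approximation with continuity correction | U ≥ 92 | 0.0463 |

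At U = 91 the uncorrected z is (91 − 64)/16.33 = 1.653, above the critical value 1.645, while the exact p-value is 0.0528. The same data would pass one version and fail the other. The uncorrected version also exceeds the stated 0.05.

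**Step 3: power of the planned test on Table 3's inputs.** Simulated trials with uniform changes, SD 13, shift 15:

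| Replicates | Exact | Uncorrected approximation |
|---|---|---|
| 400,000 | 75.4% | 77.5% |
| 200,000 (separate run) | 75.2% | 77.4% |

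The simulation standard error is below 0.1 percentage point for the larger run. Type II error is therefore about 25% (exact) or 23% (uncorrected).

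**Step 4: the difference that gives 82%.** With uniform data, SD 13 and the exact test, a difference of 15 gives 0.752, 16 gives 0.798, 16.5 gives 0.819 and 17 gives 0.839. The stated power belongs to a difference of about 16.5 mEq/L.

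**Step 5: other shapes, same SD and numbers (400,000 replicates).** These are shown for sensitivity; Table 3 names only the uniform.

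| Shape | Exact | Uncorrected approximation |
|---|---|---|
| Uniform | 75.4% | 77.5% |
| Normal | 79.2% | 81.2% |
| Logistic | 82.3% | 84.1% |
| Double exponential | 86.2% | 87.7% |

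**Step 6: SD of change.** With equal SDs of 13 at baseline and 6 months and correlation r, the SD of change is 13 × √(2(1 − r)). This equals 13 only at r = 0.5. The documents give no r, so the range below is an assumption (uniform changes, exact test, difference 15):

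| r (assumed) | SD of change | Power |
|---|---|---|
| 0.3 | 15.4 | 63% |
| 0.5 | 13.0 | 75% |
| 0.59 | 11.8 | 82% |
| 0.7 | 10.1 | 91% |

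**The case against.** The best defence is that nothing was miscalculated. The 82% comes out of a conventional large-sample approach, and the gap depends on the distribution. With normal changes it shrinks to about 1 to 3 points, and with logistic or double-exponential changes it disappears. That stands as a limit on the size of the problem. It does not rescue the printed figure, because the table names the uniform distribution and its power is not right for that case.

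A second argument is that 16 vs 8 is only a planning scenario. Sections 13.5 and 13.8 aim to include all randomized participants, and section 8.3 seeks a final function test, where feasible, from those who stop the agent early. If all 20 and 10 contributed endpoint data, exact power on the same uniform inputs would be 84.5%. That is true, but the plan attaches its 82% to 16 vs 8.

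Third, one of the cited references is titled as a crossover study, so it may hold information on repeated measurements. Its content is not in the documents. The claim is therefore a limited one: the text presents 13 as the SD of levels and does not say why it also applies to change. This gap can move power either way and is not itself evidence of low power. Over the assumed range of r its effect is larger than the 5 to 7 points at issue in Table 3.

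Finally, this is a small phase II trial that calls itself preliminary, and no design feature would change. That argues for a proportionate correction. It does not argue for leaving the wrong figure in place.

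**Conclusion.** The concern holds. On Table 3's own inputs the planned test has about 75% power (exact) or 77% (uncorrected normal approximation, true size 0.053) against the stated 82%, a shortfall of about 7 or 5 points. This rests on the uniform shape and the SD of 13 that the table itself specifies. The plan should also fix the p-value version in advance, since at 16 vs 8 the two versions disagree at U = 91.

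The missing basis for the SD of change is a gap in justification with no known direction. The 63% to 91% range depends on assumed correlations of 0.3 to 0.7 and equal variances. The correction should be made, but the point does not invalidate the design.

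**What to change.** - In section 13.1 and Table 3, replace 0.82 / Beta 0.18 with the simulated power of the planned test and name the version: 0.75 / 0.25 for the exact p-value, or 0.77 / 0.23 for the uncorrected normal approximation, noting its true size of 0.053. State the same choice in the analysis text of section 13.4.
- Under Table 3, label S1 and S2 as SDs of change from baseline and give the basis for 13 mEq/L in that role.
- Add three rows marked as an assumed range (exact test, uniform): r = 0.3, SD 15.4, power 0.63; r = 0.5, SD 13.0, power 0.75; r = 0.7, SD 10.1, power 0.91. If the sponsor has data on the correlation or the SD of change, those should replace the assumed rows.
- Add that exact power is 0.79 if changes are normally distributed.
- Label any non-compliance scenario added later as an assumption.

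The cost is wording in sections 13.1 and 13.4 and Table 3, plus a short simulation. The stated power becomes less favourable. The test, alpha and number of patients do not change.
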